Aim : To compare 2 combination DMARD therapies (MTX+SSZ+HCQ versus MTX+LEF+HCQ) in patient with early RA who have failed MTX monotherapy

Objectives :

1. To assess safety and efficacy of MTX+LEF+HCQ based combination DMARD therapy in patients with early RA failing MTX monotherapy
2. To assess safety and efficacy of MTX+SSZ+HCQ based combination DMARD therapy in patients with early RA failing MTX monotherapy
3. To compare the safety and efficacy profile of 2 combination DMARD therapy (MTX+LEF+HCQ and MTX+SSZ+HCQ)

Methodology

- A. Study design/type:** Randomized parallel group non-inferiority trial, pragmatic design
- B. Study participants:** Humans

For Participants

- a. Inclusion criteria :

Age >18 years satisfying ACR-EULAR criteria for RA

1. Polyarthritis (>4 joints)
2. Disease duration of less than 2 years
3. Patients with moderate to severe disease activity (DAS28 \geq 3.2)
4. Patients who have failed to respond to initial Methotrexate monotherapy

b. Exclusion criteria :

1. End stage disease (deformed fixed joints)
2. Patients with vasculitis, extra-articular features like interstitial lung disease
3. Contraindications to DMARD therapy (Chronic Alcoholism, Chronic liver disease, Evidence of acute/chronic infection, Chronic kidney disease, Patients with leucopenia ($<3.0 \times 10^9/l$), thrombocytopenia ($<150 \times 10^9/l$), AST/ALT $>2 \times$ upper normal value and creatinine clearance <30 ml/minute)
4. Pregnant, lactating women ; patients (both men and women) of reproductive age group unwilling for contraceptive use who have not completed the family
5. Patients unable to come for regular follow up

c. **Number of groups to be studied, their names and definitions:**

Group 1: MTX+LEF+HCQ

Group 2: MTX+SSZ+HCQ

C. Sampling

a. Sampling Population : Patients >18 years of age diagnosed with RA, attending OPD services of the Department of Clinical Immunology

b. Sample size calculation : (calculated for non inferiority trial)

Sample size has been estimated as 70 patients in each group using the N master software considering success rate as 75 % in both groups (calculated from FIN-RACo trial group, Lancet 1999 (13)) and non inferiority limit as 20% with 5 % alpha error ,statistical power of 80 % and dropout rate as 20%

c. Sampling technique: block randomization

D. Randomization details: block of 10, 1:1 random allocation.

E. Study Procedure

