A. Selection of participants: All consecutive patients of RA attending the OPD services of the department of Clinical Immunology will be included to reach a minimum sample size of in each group.

[figure not shown]
B. Patients will be assessed for eligibility and will be started on Methotrexate monotherapy initially and then only patients, who have moderate to severe disease activity inspite of 12 weeks of Methotrexate monotherapy, will be randomized to either of the 2 groups of DMARDs.

C. Allocation to groups:

Allocation concealment will be done by : Sequentially numbered, opaque, sealed envelopes (SNOSE) method

Group 1: MTX+LEF+HCQ

Group 2: MTX+SSZ+HCQ

F. Data Collection method including settings and periodicity: Patients aged above 18 years diagnosed as RA according to the 2010ACR-EULAR criteria will be screened and evaluated for inclusion in the study. The patients will be examined every 2 week interval during DMARD dose escalation & then every month for next 6 weeks of MTX and for 24 weeks for either groups.

a. Clinical evaluation:

- i. Adverse drug reactions (ADRs) – each visit
- ii. IHAQ, DAS28 - once at baseline and then at 12 weeks of MTX monotherapy and then at the end of 24 weeks treatment with either of Group 1 or group 2 drug.

b. Laboratory:

- i. Routine CBC/RFT/LFT: every 2 week interval during dose escalation & then every month for 12 weeks after starting the drug
- ii. ESR & hsCRP for disease activity evaluation: every month.
- iii. **USG** wrist, hand and feet (US-7 score)- at baseline and at 12 weeks of Group 1 or group 2 drug

G. List of variables and their measurement methods with standardization techniques:

a. (i) Independent variables

Socio-demographic profile:

- Age
- Gender

b. Outcome Variables:

Disease-related parameters –

Primary outcome measures:

- a. Disease activity (state) - DAS28

Secondary outcome measures:

- a. Functional ability – iHAQ
- b. Mean changes over time in:
 - i. Inflammatory parameters: ESR, hs-CRP
 - ii. Disease activity as per US-7 score
- c. Adverse drug reactions

Primary endpoint:

Proportion of patients in both groups achieving good response according to European League Against Rheumatism (EULAR) response criteria at the end of 12 weeks of combination therapy

Secondary endpoint:

1. Change in functional ability (Indian Health Assessment Questionnaire; iHAQ) at the end of 12 weeks of combination therapy
2. disease activity by US7 score at 12 weeks

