2. Oral low dose Glucocorticoids (GC) - 7.5 mg/d for 4 weeks followed by 5 mg/day for 2 weeks followed by 5mg on alternate day for 2 weeks – as a bridge therapy. Thereafter, it can be given if disease flares (patient being symptomatic with continued DMARD therapy), with the maximum dose being 7.5mg/day.
3. Intra articular steroids-will be allowed during the study, as per severity of patient’s symptoms. The number of intraarticular injections required in each group will be calculated.

DMARD dosages used are:

For all patients as a standard protocol for management of all patients with RA :

1. **MTX** – starting dose 10 mg/week orally for 2 weeks → 15mg / week for 2 weeks 20 mg/ week for 2 weeks → 25mg/ week → assessment of response to MTX after 6 weeks (at the end of 12 weeks after starting MTX)
2. In patients , not tolerating adequate doses of oral MTX in the form of nausea, vomiting, the following strategies will be adopted- 1) dose will be split into two 2) oral MTX will be converted to im formulation.
3. T. Ondansetron 4mg twice a day for 2 days a week will be allowed in the study if patient has nausea or vomiting with MTX.
4. T. Folic acid 5 mg twice a week

Those not achieving adequate response to a maximum permissible dose of MTX (25 mg / week) ie. DAS28ESR >3.2 will be enrolled in the study after randomization:

For **Group 1**

1. T. MTX will be continued at 25mg/week
2. T. folic acid 5 mg twice per week
3. T. LEF -10 mg/day starting dose for 2 weeks → 20mg /day
4. T. HCQ 200 mg/day at night

For **Group 2**

1. T.MTX will be continued at 25mg/week
2. T. Folic acid 5 mg twice a week
3. T.SSZ 500mg once a day for 7 days → 500mg twice a day for 7 days →
500mg thrice a day for 7 days → 1gram twice a day
4. T. HCQ 200mg/day at night

Note: During the course of the study any patients developing extra-articular manifestations requiring different mode of therapy will be excluded from study (but intention to treat analysis will be used for analysis of results).

STATISTICAL ANALYSIS PLAN (SAP)

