The trial is designed as a non-inferiority pragmatic trial. The assessment will be done in unblinded fashion by the researcher. Arbitrarily considering EULAR good response rate (primary endpoint) of 75% with SSZ based triple regimen (tREACH and TICORA study) and non-inferiority margin of $\Delta = (-20\%)$ for LEF, a sample size of 140 (70 in each group) was determined using nMaster sample size calculator (version 2 software) using 2-sided confidence levels (CI) of 95%, power of 80% and dropout rate of 20%.

Data will be analyzed using SPSS (IBM pasw statistics, version 19.0) for windows. For quantitative data [DAS28ESR, iHAQ], normality of distribution will be checked by Shapiro-Wilks W test. Continuous data was presented as median and interquartile range (IQR₂₅₋₇₅) / mean with SD as appropriate. Mann-Whitney U test / Students t test will be used for comparison between median/ mean of 2 groups respectively. Qualitative or categorical variables (such as EULAR good response) will be described as proportions and will be tested using Chi-square. Odds ratio (OR) – odds of achieving the outcome (treatment response) in patients exposed to LEF in comparison to patients not exposed to LEF (SSZ group) along with 95% confidence interval and p-value will be used to study the statistically significant difference in treatment outcome between 2 groups. P-value of <0.05 was considered as significant.

The primary endpoint will be analyzed by both intention-to-treat (ITT) and per-protocol (PP) analysis. The rest of the parameters will be analyzed by ITT analysis only. Patients who do not complete the study, the last observation will be taken as their outcome for ITT analysis. For missing data, the last available readings will be carried forward in case of patients who are not available for the endpoint assessment. Non-inferiority testing will be done by using a 95% confidence interval (CI) of the difference between the proportions of patients achieving the primary endpoint between 2 groups. Extension of CONSORT 2010 statement will be used for reporting of non-inferiority of the LEF group.

DATA COLLECTION PROFORMA

CODE NO:

Date of enrollment:

Name/ age/ sex/ CCR no :

Contact number

Disease duration:

Co-morbid conditions (with duration):

Personal history (habits/addictions):

Treatment history:

Family history:

Baseline Investigations:

RF:

HIV:

HBsAg:

HCV:

Anti-CCP:

Mantoux test:

Drug

Dose

since when

Side effects

1

2

3

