| | Baseline | 4mo | 5mo | 6mo |
|---------------|-----------------|------------|------------|------------|
| IA Steroids | | | | |
| Oral steroids | | | | |

| | Baseline | 4 week | 8 week | 12 week | 16 week | 20 week | 24 week |
|--------------------------|-----------------|---------------|---------------|----------------|----------------|----------------|----------------|
| TJ28 | | | | | | | |
| SJ28 | | | | | | | |
| VAS | | | | | | | |
| ESR | | | | | | | |
| hsCRP | | | | | | | |
| DAS28 | | | | | | | |
| iHAQ | | | | | | | |
| Morning stiffness | | | | | | | |

| | | | | | | | |
|--------------------------------|--|--|--|--|--|--|--|
| Extraarticular features | | | | | | | |
| Adverse drug reactions | | | | | | | |

FOLLOW UP INVESTIGATIONS

| Investigations | Baseline | 4W | 8W | 12W | 16W | 20W | 24W |
|-----------------------|-----------------|-----------|-----------|------------|------------|------------|------------|
| Hb | | | | | | | |
| TLC | | | | | | | |
| DLC | | | | | | | |
| MCV | | | | | | | |
| Platelets | | | | | | | |
| Peripheral smear | | | | | | | |
| Urine albumin | | | | | | | |
| Microscopy | | | | | | | |
| Blood urea | | | | | | | |
| Sr. Creatinine | | | | | | | |
| Bilirubin (T/D) | | | | | | | |
| AST/ ALT | | | | | | | |
| ALP/GGT | | | | | | | |
| Total protein /Alb | | | | | | | |
| CPK / LDH | | | | | | | |
| Sugar (AC/PC) | | | | | | | |
| CH/TG/HDL/LDL | | | | | | | |
| CT/USG/MRI | | | | | | | |
| ECG/ECHO | | | | | | | |

| US7 Score | | Baseline | 12 week | 24 week |
|------------------|-----------|-----------------|----------------|----------------|
| Synovitis | GS | | | |
| | PD | | | |
| TS | GS | | | |
| | PD | | | |
| Erosion | GS | | | |

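### Flare steroids and joint injections before the week-12 visit have no place in the analysis plan, and the form's steroid table omits half of combination therapy, which half depending on an unstated time origin

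*Combined protocol and SAP*

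**What the plan says.** The primary endpoint (protocol, Primary endpoint) is the proportion "achieving good response according to European League Against Rheumatism (EULAR) response criteria at the end of 12 weeks of combination therapy". The trial is a pragmatic non-inferiority comparison, and the SAP states that the researcher assesses outcomes unblinded.

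The protocol's list of permitted concurrent treatments, item 2, gives an oral steroid bridge of 4 + 2 + 2 = 8 weeks. It then says of oral steroid: "Thereafter, it can be given if disease flares". When the bridge starts (at methotrexate start or at randomisation) is not stated. Item 3 allows intra-articular steroid during the study according to symptoms and adds: "The number of intraarticular injections required in each group will be calculated". No matching count is planned for oral steroid, and neither item sets an interval before the week-12 visit.

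On analysis sets the SAP says: "The primary endpoint will be analyzed by both intention-to-treat (ITT) and per-protocol (PP) analysis". The per-protocol set is not defined. Missing outcomes are filled by last observation carried forward. Steroid use does not appear in the analysis text.

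In the data collection proforma, the table for intra-articular and oral steroids has the columns "Baseline | 4mo | 5mo | 6mo". The DAS28 table on the same form runs every 4 weeks from baseline to week 24.

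**The concern.** A patient whose DAS28 is low at week 12 because of a flare course or a recent injection is counted as a good responder to the randomised combination. The arm with more non-responders has more patients whom rescue could convert, so rescue tends to draw the two response rates together. In a superiority trial that would be conservative. Here it works in favour of the claim the trial is designed to make. Unblinded care driven by symptoms also leaves room for rescue to differ between arms.

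A treatment-policy comparison, which takes the outcome whatever rescue was given, is a legitimate primary analysis in a pragmatic trial. However, the plan does not say that this is its choice. It offers no second analysis to show how far the result depends on steroids, and the form may not hold the data to run one.

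**Working it through.** **1. The plan's own figure.** The protocol's inputs are "considering success rate as 75 % in both groups" and "non inferiority limit as 20% with 5 % alpha error ,statistical power of 80 % and dropout rate as 20"%. With n = (z_α + z_β)² × 2 × 0.75 × 0.25 / 0.20²:

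- One-sided 5%: (1.645 + 0.842)² × 0.375 / 0.04 gives 58, and 58 × 1.2 = 70. This reproduces the stated 70 per group.
- The SAP's 2-sided 95% interval (one-sided 2.5%): (1.960 + 0.842)² × 0.375 / 0.04 gives 74, and 74 / 0.8 = 93.

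The mismatch between the two is a separate matter. The illustration below takes 70 per arm and the SAP's 95% interval.

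**2. What the steroid table covers.** Methotrexate alone lasts 12 weeks, about 3 months.

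| Months counted from | Months 4, 5, 6 fall at | Part of combination therapy with no steroid column |
|---|---|---|
| Randomisation | about combination weeks 16-24 | weeks 1-12 (primary window) |
| Methotrexate start | about combination weeks 4, 8, 12 | weeks 13-24 (run-up to the 24-week secondary endpoint) |

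Under either origin, half of the 24 weeks has no column, so the table does not support the promised injection count for all of combination therapy.

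**3. When flare steroid can occur.** If the bridge starts at randomisation and is given, flare oral steroid is possible from about week 9, so about weeks 9-12 of the primary window. If it starts with methotrexate, the 8 weeks end before randomisation and flare steroid is possible throughout the window. Injections are possible throughout in both cases.

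**4. Direction and size, as an illustration.** Assumptions not in the documents: response without rescue is 75% with sulfasalazine (the plan's rate) and 55% with leflunomide (exactly at the margin), and rescue converts a share f of all non-responders.

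- Sulfasalazine: 0.75 + 0.25 f_S. Leflunomide: 0.55 + 0.45 f_L.
- Difference: -0.20 + 0.45 f_L - 0.25 f_S. With equal f this is -0.20 + 0.20 f.
- At these rates the difference shrinks unless f_S exceeds 0.45/0.25 = 1.8 times f_L.

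The table gives the exact binomial probability that the lower 95% limit lies above -20 points, at 70 per arm:

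| f (leflunomide / sulfasalazine) | Response rates | Difference (points) | Newcombe | Wald |
|---|---|---|---|---|
| 0 / 0 | 55% v 75% | -20 | 2.9% | 2.4% |
| 10% / 10% | 59.5% v 77.5% | -18 | 4.9% | 4.5% |
| 20% / 20% | 64% v 80% | -16 | 8.3% | 7.8% |
| 30% / 30% | 68.5% v 82.5% | -14 | 14.0% | 13.4% |
| 20% / 10% | 64% v 77.5% | -13.5 | 14.4% | 13.7% |

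With 56 completers per arm (70 × 0.8) the pattern is the same: on the Wald interval, 2.6%, 4.3%, 7.3%, 11.9% and 12.0%.

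**5. What counting rescue as failure does.** If 20% of would-be responders in each arm are rescued as well, the rates become 0.75 × 0.8 = 60% and 0.55 × 0.8 = 44%. The difference is again -16 points, and the chance of declaring non-inferiority is 7.0% (Newcombe, 70 per arm). With equal arms, power is 79% at 75% response and 71% at 60%.

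**The case against.** Four points can be made for the plan.

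- **The record may cover the primary window.** A reader might infer that rescue before week 12 goes unrecorded. The documents do not establish this. A table that skips months 1-3 fits a count from methotrexate start at least as well, and the primary window is then covered. The opposite reading also has support: the protocol times its response assessments from allocation, and the other follow-up tables use 12- and 24-week columns. What stands is an undefined origin and a missing half. The proforma's short general drug list has no visit columns, and nothing assigns steroids to it.
- **The probabilities are not type I errors of the plan.** A reader might take 4.9% to 14.0% as the plan's false-positive rate. For a treatment-policy comparison, true differences of -18 to -13.5 points lie inside the margin, so declaring non-inferiority there is correct. The figures are errors only for the question of what the drugs do without rescue, which the plan does not adopt. This stands in full.
- **The size has no anchor.** The documents give no rescue rate, and f combines the chance of rescue with the chance that rescue converts. f = 30% needs, for example, 60% of non-responders rescued and half of those converted. Nor do the documents show that rescue would be more frequent in the weaker arm. This stands too. Only the direction is firm, and only when conversion is equal or higher with leflunomide, or not too much lower (step 4).
- **Rescue-as-failure is not a clean check.** It also fails patients who would have responded anyway, it can shrink the difference by itself (step 5), and it lets unblinded discretion over rescue decide the outcome. A reader might want non-inferiority called robust only if both analyses meet the margin; this objection tells against such a rule.

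**Conclusion.** The point holds as a gap in analysis and recording. Flare oral steroid and joint injections can fall just before the primary assessment, no analysis takes them into account, and the undefined per-protocol set gives no stated protection. The steroid table omits half of combination therapy under either time origin. The documents do not show that rescue is hidden in the primary window, or that the planned primary analysis is invalid.

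The size cannot be derived from the documents. Under the assumed 75% v 55% and equal conversion of 10% to 30%, the chance of declaring non-inferiority rises from 2.9% to between 4.9% and 14.0%, read as an error about the drugs without rescue. The change is worth making because it is cheap and lets readers see how far the result depends on steroids.

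**What to change.** 1. **Form.** Replace the steroid table with 4-weekly columns from randomisation to week 24, matching the DAS28 table. For oral steroid record date, dose and indication (bridge or flare); for each injection record date and joint. Without the indication, the single oral-steroid row cannot separate scheduled bridge from flare use.
2. **Reporting.** Tabulate flare oral steroid and injections by arm for weeks 0-12 and 12-24.
3. **Analysis.** State that the primary analysis is treatment-policy, and keep it. Add one prespecified supportive analysis of the week-12 endpoint, in the ITT and per-protocol sets (the latter needs a definition). In it, patients given flare oral steroid or an intra-articular injection between randomisation and week 12 count as not achieving good response; scheduled bridge use does not count. Show it with its 95% confidence interval beside the primary result, with no rule that both must meet the margin.
4. **Text.** State when the bridge course starts. No change to the rescue rules is proposed.

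The cost is one changed form table and one extra analysis. That analysis will have lower response rates and less power (about 71% rather than 79% if response falls to 60% in both arms), and it will count as failures some patients who would have responded anyway. It should be read as supportive for that reason.

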3. Safety of study medications (adverse drug reactions) during study period (till 24 weeks)
4. Proportion of patients achieving good EULAR response at the end of 24 weeks of combination therapy

Assessment of treatment response

The disease activity will be reassessed at the end of 12 and 24 weeks of random group allocation. The treatment response will be graded according to EULAR response criteria

Radiological assessment of disease activity

Musculoskeletal Ultrasound (**US-7 score**) will be performed in all patients in non blinded manner by the researcher

Clinical Evaluation :

- a. Demography: Age/Sex, ethnicity
- b. Detailed history and examination will be done for all patients
- c. Baseline evaluation of patient

Disease Activity: Indian Health associated questionnaire (IHAQ), Disease Activity Score-28 (DAS28)

Damage: Joint: Loss of motion, Deformity, Mal-alignment

- d. Extra-articular: Sicca symptoms & signs, sub cutaneous nodules, evidence of Interstitial Lung Disease (ILD), peripheral neuropathy, scleritis/episcleritis

Laboratory investigations

- i. **Routine:** Complete blood count (CBC), Erythrocyte Sedimentation Rate (ESR), Sugar (FBS/PP2BS), Liver Function Test (LFT), Renal function test (RFT), Mantoux Test, Viral markers (HIV, HBsAg, Anti HCV), urine analysis, Thyroid function test (TFT)

ii. **Ultrasound (USG)** wrist, hand and feet (US-7 score)

Immunological: High sensitivity C-reactive protein (hsCRP), Rheumatoid Factor (RF), Anti-CCP antibody (ACPA) in all participants .

After baseline evaluation, all consecutive patients with RA will be started on MTX monotherapy unless contraindicated. Patients not responding adequately to MTX monotherapy (DAS28 \geq 3.2) at the end of 12 weeks will be randomized to either of the 2 groups by block randomization after written informed consent.

- MTX+LEF+HCQ- Group 1
- MTX+SSZ+HCQ- Group 2

Concurrent treatment with the following drugs will be allowed during the study as per severity of symptoms and in cases of breakthrough pain:

1. Non-steroidal anti-inflammatory drugs (NSAIDs) - Tablet Diclofenac sodium 50mg twice a day (will be given for minimum duration) and if given on “as and when required” basis, patient will be asked to maintain an NSAID diary so as to know their requirement.

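### Good responders removed for extra-articular disease between weeks 12 and 24 count as week-24 good responses without being assessed, and their later adverse reactions have no stated route into the data

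*Combined protocol and SAP*

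**What the plan says.** The Note after the Group 2 doses, at the end of the protocol, reads: "any patients developing extra-articular manifestations requiring different mode of therapy will be excluded from study (but intention to treat analysis will be used" for the results). It neither asks for visits after removal nor says how such a patient's response is scored.

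The SAP, third paragraph, supplies the score: "Patients who do not complete the study, the last observation will be taken as their outcome for ITT analysis", and "the last available readings will be carried forward in case of patients who are not available for the endpoint assessment". The primary endpoint is analysed by both ITT and per-protocol, but "The rest of the parameters will be analyzed by ITT analysis only".

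Two secondary endpoints run to week 24. Number 4 is "Proportion of patients achieving good EULAR response at the end of 24 weeks of combination therapy". Number 3 is drug safety over the same period.

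On timing, the section on assessment of treatment response says "The disease activity will be reassessed at the end of 12 and 24 weeks of random group allocation". Section F collects adverse reactions at each visit and plans examinations "every month for next 6 weeks of MTX and for 24 weeks for either groups". The data collection proforma also has DAS28 columns at weeks 4, 8, 16 and 20. It does not say whether these count from randomisation.

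**The concern.** Naming ITT settles who is in the denominator. It does not create the missing measurement. The Note takes the patient out of the study, not only off study drug, so the plan itself causes the week-24 value to be missing and then fills it with an older one. If that older value is a good response, the patient is recorded as a week-24 success after leaving the regimen for a new disease manifestation. Week 24 has no per-protocol analysis and no sensitivity analysis that would show this.

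Safety raises the same issue. Reactions are collected at visits, and a removed patient has no stated visits. Objectives 1 and 2 ask for the safety and efficacy of each regimen separately, so an error in one arm's rate matters even if the comparison between arms is unaffected.

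**Working it through.** **Inputs.** From the documents: 70 patients per group and a 75% success rate (sample size calculation), with the last-observation rule and the ITT-only rule (SAP). Assumed, because the documents give neither: *k*, the number of good responders removed from an arm between weeks 12 and 24, and *f*, the share of them who are truly not good responders at week 24.

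**1. The plan's own figure.** n per arm = (z for alpha + z for power)² × (2 × 0.75 × 0.25) / 0.20². With one-sided 5% and 80% power: (1.645 + 0.842)² ≈ 6.18, times 0.375/0.04 = 9.375, gives 58. Adding 20% gives 58 × 1.2 = 69.6, or 70. The stated figure is reproduced on that basis. The SAP's two-sided 95% interval (one-sided 2.5%) would need 74 before dropout. That is a separate matter; here 70 serves only as the denominator.

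**2. The rules applied in order.** A patient is a good responder at week 12, develops extra-articular disease needing other therapy at, say, week 15, and is removed. The patient has not completed, so the last observation becomes the ITT outcome. That observation is a good response, and it is entered at week 24.

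**3. Age of the carried value at week 24.** With reassessment at weeks 12 and 24 only: 24 − 12 = 12 weeks. If the proforma's DAS28 columns are used after randomisation, it may come from week 16 or 20: 24 − 16 = 8 or 24 − 20 = 4 weeks. In every case week 24 itself is unobserved.

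**4. Size in one arm.** Overstatement in points = 100 × k × f / 70.

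| k | f = 0 | f = 50% | f = 100% |
|---|---|---|---|
| 1 | 0.0 | 0.7 | 1.4 |
| 2 | 0.0 | 1.4 | 2.9 |
| 3 | 0.0 | 2.1 | 4.3 |

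If 75% of removed patients were good responders, k = 1, 2, 3 corresponds to k/0.75 = 1.3, 2.7, 4.0 removals, or 1.9%, 3.8%, 5.7% of an arm.

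**5. Effect on the week-24 difference, LEF minus SSZ.** Take 53/70 true responders in each arm (75% of 70 is 52.5), f = 100%, and Wald 95% intervals. With no removals the difference is 0.0 (−14.2 to 14.2).

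- k = 1 in LEF only (54 v 53): +1.4 (−12.6 to 15.5). In SSZ only: −1.4 (−15.5 to 12.6).
- k = 3 in LEF only (56 v 53): +4.3 (−9.5 to 18.0). In SSZ only: −4.3 (−18.0 to 9.5).
- Equal numbers in both arms: 0.0.

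**6. Week 12.** Under the text schedule, the last DAS28 before week 12 is the one at randomisation. It shows no change since randomisation and, by the entry rule, still indicates moderate to severe activity. A removal before week 12 is therefore scored as a non-response. If the proforma's week-4 and week-8 columns are used after randomisation, an early good response could be carried into week 12.

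**7. Safety.** The triggering event can be recorded at the visit where it is found. For reactions after that visit, the documents describe no collection. This is an inference from silence.

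**The case against.** The wording may be loose: exclusion from the study may mean only leaving the study regimen, and the statement that disease activity is reassessed at 12 and 24 weeks from allocation could be read as covering every randomised patient. That reading is possible. But the general statement does not mention removed patients and does not override an explicit exclusion. If follow-up is intended, the fix only writes it down.

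The number affected is probably small. Entry requires disease of less than 2 years and excludes vasculitis and extra-articular features such as interstitial lung disease. A patient must then develop such disease in a 12-week window, need other therapy for it, already be a good responder, and lose response. DAS28 may stay low while extra-articular disease appears, so *f* could be well below 100%. All of this stands, and it is why the priority is minor.

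This is also one case of a general last-observation rule in a plan that allows 20% dropout, and the fix leaves other carried values untouched. That stands too. The difference is that here the protocol itself ends follow-up in patients who might otherwise attend.

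An observed week-24 value would partly reflect the new therapy, whereas the endpoint concerns combination therapy. This is why a non-response sensitivity analysis is needed alongside it.

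A reader might infer more: that these patients are dropped from the analysis, that one arm is favoured, or that the primary non-inferiority test is biased. The documents support none of these. The Note keeps the patients in the ITT set, no removal rate by arm is given, and the text schedule scores removals before week 12 as non-responses.

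**Conclusion.** The point holds for one secondary efficacy endpoint and for safety follow-up. As written, a good responder removed between weeks 12 and 24 is counted as a week-24 good response without being assessed. This overstates that arm's rate by at most 1.4 points per patient with 70 per arm, and by nothing if the patient is still a responder. Reactions after removal may be missed. The size depends on the assumed *k* and *f*, and the direction between arms is unknown. Even three such patients in one arm move the difference by 4.3 points at most, against an interval half-width of about 14.

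The week-12 primary endpoint is unaffected under the text schedule. That is conditional: if the proforma's week-4 and week-8 DAS28 readings are used after randomisation, an early good response could be carried into it. Minor priority.

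**What to change.** **Protocol Note.** Replace the exclusion with: *study drug is stopped or changed as clinically needed; unless consent is withdrawn, the patient stays in the study and attends scheduled visits to week 24 (DAS28, iHAQ, ADRs), with the date and drug of any change recorded.* Treatment of the extra-articular disease is unchanged.

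**SAP, week 24.** Use the observed value for these patients and carry forward only if the visit was missed. Add a sensitivity analysis scoring them as not achieving good response.

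**SAP, week 12.** Score patients who meet the Note before week 12 as not achieving good response. This preserves the text-schedule result and closes the proforma route. Using their observed week-12 values instead would alter the primary ITT outcome, since a response on non-study therapy could then count as a success.

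**Cost.** A wording change, a few SAP sentences, one sensitivity analysis, and follow-up of a few extra patients at monthly visits already planned. Observed week-24 values will partly reflect the new therapy and could move the rate either way. Reactions after the switch are harder to attribute to study medication, which is why the date and drug of each change should be recorded.
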